Appendix 2 details the outcome measures to be analysed and their associated models.

A causal mediation analysis (including craving, MoCa, QUIDS-SR and WSAS as mediators in separate models) will be implemented using a counterfactual framework to include a treatment/mediator interaction and covariates, based on univariable path screening, and with bias corrected bootstrapped estimates.

6.8 SUBGROUP ANALYSES

Subgroup analyses will be conducted for the primary objective/outcome on the following:

- Using cocaine (Yes/No)
- Length of time in treatment (less than one month/one month or longer)
- Benzodiazepine use past month to admission (Yes/No)
- CGI-S (Mild/Severe)

6.9 SENSITIVITY ANALYSES OR MODEL TESTING

Sensitivity analysis will be conducted on the primary analysis model including the variables that were identified as predictors of missingness as covariates in the model.

Additionally, sensitivity analysis may be required around any assumptions made for the primary analysis (e.g. outliers, data distributions) but will only be conducted if necessary. This will include a best-case worst-case analysis on the self-report missing data on the primary outcome. Best case would assume that patients did not use during any missing time periods and worst case would assume that they did use substances to evaluate any impact the imputed data may have had on the results.

Furthermore, the confidence of the reliability of the self-report will be checked by conducting a best-case worst-case sensitivity analysis on the UDS missing data for the TLFB outcomes.

For those who have a missing UDS, we will assume all missing as negative for one dataset and then for another dataset assume all missing as positive. Utilising this best –worst case scenario will provide a range of values between which the real outcome is likely to lie. The width of this range is likely to be influenced by many factors (including the COVID pandemic and not being able to collect the UDS).

Primary and secondary analysis will be conducted on an ITT basis (including all those randomised to be analysed. Sensitivity analysis may be conducted, if necessary, on protocol deviations or eligibility violations by removing them from the analysis set. This includes protocol deviations (but is not limited to) such as;

- Patients not receiving randomized allocation (per protocol analysis)
- Patients not receiving treatment within 7 days (per protocol analysis)
- Ineligible patients being randomised (mITT analysis)

Sensitivity analysis will be conducted on the patient's months in treatment (for current episode) at baseline by running the model including the variable as a factor.

Additionally, sensitivity analysis of the patient's preference of BUP-SL or MET will be conducted again by running the model including that variable as a factor. This will be conducted given that there is an adequate sample of data per group at each level of the variable (BUP-SL or MET) a sample of 50% – 60% in the MET group will indicate that we will run this sensitivity analysis.

Sensitivity analysis will be conducted truncating at 14 days at the end of the TLFB data (i.e. day 8 – day 154) to assess the impacts of using the medical notes due to the administration error highlighted in section 5.2.

Furthermore, there will be a sensitivity analysis around the week 'Grace period' of the primary outcome where we will include all TLB data from day 0 to day 168.

COVID-19

A sensitivity analysis around the impact of the COVID-19 pandemic has been considered. The biggest impact the pandemic has had on the trial, to date, is the pause in recruitment which occurred March 2020 to July 2020, however, the trial is currently back recruiting in all sites. Some of the psychosocial intervention was delivered remotely (by telephone and video call) and some data collection was collected remotely during this time. The paper will include a summary of milestone dates such as the date COVID-19 was declared a pandemic by the World Health Organisation, date the Government imposed lockdown and dates the trial paused and restarted recruitment.

In addition, during the pandemic, changes to the distribution of medication for those in the oral arms of the study occurred. National clinical guidance was issued on 22 May 2020

indicating that rather than daily medication collection participants were to collect weekly and not be observed whilst taking them. This may have had an impact on some participants as they had access to more medication and more freedom with these (i.e. there was choice as to whether to take medication as directed). This could result in participants in these groups being more likely to disengage from treatment and relapse. However, subsequent guidance has recommended that supervision and dispensing interval should return to be determined on a case-by-case basis and informed by risk assessment [8]. This advice may change again in the event of a substantial increase in Covid-19 infection incidence.

Although these changes may have had an impact, investigators have no reason to believe that this will affect any signal (or no signal) detected.

However, baseline characteristics will be summarised by enrolment period (pre Covid-19, during Covid-19, post Covid-19) to assess if there are any relevant differences in the recruited population relative to the pandemic periods [9]. If deemed necessary sensitivity analysis adding 'pandemic enrolment period' into the model will be run and if found to be significant subgroup analysis may be conducted.

Finally, as indicated in section 4.6 an evaluation of missing data will be conducted prior to analysis. Missing data will be assessed by 'pandemic enrolment period' to check whether there are any differences of missingness caused by the pandemic. Missing data will be handled in line with section 4.6 of this SAP with additional guidance from recent literature on dealing with missing data in a pandemic [10].

One element of study processes which have been largely impacted by COVID is the data collection of the UDS, which will have an impact on the primary outcome. Essentially this is seen as missing data but it doesn't impact the level of missing data just the reliability of the self-report and occurs in both arms of the trial. The trial originally planned to collect UDS tests every two weeks however the following occurred;

Table 3: Summary of UDS data collection during trial following COVID-19 impacts

Site	Date	UDS data collection	
		TAU arm	Intervention arms
All	Up to 2 nd April 2020	every 2 weeks	every 2 weeks

All	2 nd April 2020 – 12 th June 2020	Not collected	Not collected
South London	04.05.2020	Not Collected	Monthly
	12.06.20	Monthly	Monthly
Newcastle	07.05.2020	Not Collected	Monthly
	29.06.20	Monthly	Monthly
Manchester	13.07.20	Monthly	Monthly
West Midlands	03.07.20	Monthly	Monthly
Tayside opened for recruitment on	27.07.20	Monthly	Monthly

As at the point of writing the SAP the trial is continuing to collect UDS monthly (on the larger visit weeks 4,8, 12, 16,20, 24). As there is little study data that hasn't been impacted by this and it has affected both arms simultaneously sensitivity analysis around this is not required. If any further changes during the ongoing pandemic occur that the investigators feel will impact any signal detected this will be conducted as exploratory post-hoc analysis.

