6.1 Investigational medicinal product

Bup extended-release injection (XR-Bup in this protocol) is licenced in the USA under the name Sublocade®. It is used for the treatment of moderate to severe OUD in patients who have initiated treatment with a transmucosal Buprenorphine product. The product is currently unlicensed in the EU. The injection is presented as a sterile, clear, viscous,

colourless to yellow amber solution in a single dose, pre-filled syringe with a 19 gauge 5/8th inch safety needle.

Bup in XR-Bup is dissolved in the ATRIGEL® delivery system. This system delivers the drug at a controlled rate over a 1-month period. The depot injection provides sustained plasma levels of Bup sufficient to block the subjective effects of exogenous opioids after a single dose and even more complete blockade after two monthly doses. The product is available in dosage strengths of 100mg/0.5ml and 300mg/1.5ml Bup. It is administered as a monthly subcutaneous injection into abdominal tissue.

Indivior will be responsible for the manufacture of the product and import into the UK. Sharp Clinical Services (UK) are contracted by Indivior to label and final Qualified Person (QP) release the product prior to distribution to investigational sites. The Simplified Investigational Medicinal Product Dossier (sIMPD), US Prescribing Information and Investigator Brochure (IB) provides further information.

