8.3 Selection of participants

All participants for EXPO will be recruited from specialist NHS addictions treatment programmes in community settings and already in receipt of opioid substitution therapy. Patients will consent prior to any screening procedures and will be randomised at a minimum of 24 hours post consent.

Post- randomisation treatment is summarised as follows:

Participants randomised to standard-of-care oral maintenance

Participants who are allocated to oral opioid pharmacotherapy will receive Bup/Met according to medical screening and informed by patient preference, following each site's usual screening, induction/stabilisation and maintenance dosing and medication dispensing procedure. There will be an additional requirement to attend the clinic after 2 weeks and then at least monthly to complete research measures and a urine drug screen procedure.

Met participants randomised to XR- Bup

Met participants will firstly be converted to Bup by following the sites local clinical procedure. Once stabilised on Bup, participants will require a period of at least 3 days on 8mg-24mg of Bup before they can receive the first dose of XR- Bup. The last dose of Bup is to be taken 1 day prior to the first dose of XR- Bup. Participants should receive their first injection of XR-Bup within 7 days of randomisation.

Bup participants randomised to XR- Bup

If the participant is prescribed less than 8mg of Bup there will be a minimum 3-day lead-in on 8mg Bup prior the first dose of XR-Bup. Participants who were previously prescribed 8mg or higher BUP can receive XR-Bup upon agreement of a suitable time with the participant and EXPO research team. The last dose of Bup is to be taken 1 day prior to the first dose of XR- Bup. Participants should receive their first injection of XR-Bup within 7 days of randomisation.

For all participants if during the transition period, the participant decides not to receive XR- Bup or clinical judgement deems it unsuitable to continue the participant will be withdrawn from the trial (ITT population).

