4.5 PROTOCOL VIOLATIONS

Definition of protocol violations and deviations. Violation is an intended failure to adhere to the protocol such as wrong treatment being prescribed or administered or incorrect data being collected and documented. A protocol deviation is an unintended failure to adhere to the protocol and examples include errors in applying inclusion/exclusion criteria or missed follow-up visits due to error. Per protocol analysis is not planned for the study but deviations and violations will be monitored and reported throughout the study and detailed descriptively in the analysis report. If protocol deviation occurrences rise above 10% then sensitivity analysis as detailed in section 6.5 will be conducted. Some examples of protocol deviations which might occur in this study include;

- Patients not receiving randomised allocation
- Patients not receiving treatment within 7 days
- Ineligible participants being randomised

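### The optional per-protocol exclusions in SAP 6.9 fall almost entirely on the XR-Bup arm, so they do not compare like with like, and SAP 4.5 and 6.9 disagree on whether and when they are run

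*SAP*

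**What the plan says.** The primary analysis is intention to treat (SAP 3.1, Analysis set; SAP 6.9). SAP 6.9 then provides: "Sensitivity analysis may be conducted, if necessary, on protocol deviations or eligibility violations by removing them from the analysis set". The list that follows is open ("This includes protocol deviations (but is not limited to) such as"). It names two exclusions as per-protocol analyses, "Patients not receiving randomized allocation (per protocol analysis" and "Patients not receiving treatment within 7 days (per protocol analysis". A third, for ineligible participants, is labelled mITT and can affect either arm.

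SAP 4.5 reads differently. It states "Per protocol analysis is not planned for the study", and its next sentence adds "If protocol deviation occurrences rise above 10% then sensitivity analysis as detailed in section 6.5 will be conducted". SAP 6.5 is Descriptive Statistics; the exclusions are in 6.9.

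On who enters the trial, inclusion criterion 3 (Protocol 8.1) requires current enrolment on methadone or a buprenorphine product, and Protocol 8.3 describes all participants as "already in receipt of opioid substitution therapy". The 7-day start appears in Protocol 8.3 only for the first XR-Bup injection, with no equivalent for the oral arm. Participants allocated to XR-Bup who do not proceed during the transition are withdrawn from the trial but labelled as part of the ITT population. Adherence is otherwise reported only descriptively (SAP 4.4).

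**The concern.** A post-randomisation exclusion keeps the comparison fair only if it would select the same kind of participant from each arm. Here the test is whether the participant started a new treatment. One arm has to clear that hurdle; the other normally meets it by carrying on. The oral-arm counterparts of the XR-Bup non-starters cannot be identified and stay in.

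These two exclusions are the only named re-estimates of the primary result that depend on treatment received. If the result agrees with ITT, that is weak reassurance. If it shows a larger effect, it could be read as support for superiority when it reflects who was removed. The SAP also does not settle in advance whether the check is run, or which deviations count, because 4.5 and 6.9 give different rules and the list is open. The research and clinical teams in this open-label trial are unblinded (Protocol 5.2).

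**Working it through.** The plan gives no figure for this point, so there is none to reproduce. The check is a reading of the text followed by an illustration.

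**1. Who can fail each test**

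- Oral arm, allocation: participants are already on Met or Bup, and switching between comparators is permitted (Protocol 6.2), so a switch is not a failure of allocation.
- Oral arm, 7 days: no start rule is written.
- XR-Bup arm, by route in Protocol 8.3: methadone participants convert and spend at least 3 days on Bup; those below 8 mg Bup have a lead-in of at least 3 days; those at 8 mg or above need neither, but must still agree a time, attend and accept the injection. Protocol 8.3 foresees refusal or clinical unsuitability at this stage.

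Both exclusions therefore fall almost entirely on XR-Bup.

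**2. Size under assumed rates**

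Inputs from the documents: control abstinence 0.6, 161 outcome days, 23% target difference (SAP 4.1). Target: 0.6 × 161 × 0.23 = 22.2 days.

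Assumed: no true effect, non-starters abstinent on 30% of days, all participants followed throughout, a share f removed from XR-Bup and nobody from the oral arm. The retained XR-Bup rate is (0.60 − f × 0.30)/(1 − f).

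- f = 5%: 0.585/0.95 = 0.6158; (0.6158 − 0.60) × 161 = 2.5 days, about 11% of the target.
- f = 15%: 0.555/0.85 = 0.6529; (0.6529 − 0.60) × 161 = 8.5 days, about 38% of the target.

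**3. Direction**

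Let r be the mean abstinent days of removed participants divided by that of retained ones. Under a true ratio of 1, the per-protocol ratio is 1/(1 − f(1 − r)). With f = 10% and a control mean of 0.6 × 161 = 96.6 days:

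| r | ratio | days |
|---|---|---|
| 0.25 | 1.081 | +7.8 |
| 0.50 | 1.053 | +5.1 |
| 0.75 | 1.026 | +2.5 |
| 1.00 | 1.000 | 0 |
| 1.25 | 0.976 | −2.4 |

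**4. The pooled trigger**

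If the 10% in SAP 4.5 is a share of the 304 participants, it is 30.4 people. If all were in XR-Bup, that is 30.4/152 = 20% of the arm. At f = 20%, r = 0.5 gives a ratio of 1.111, or +10.7 days.

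**5. What a complier-average effect needs**

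In its simplest form it is the ITT difference in days divided by the proportion starting XR-Bup. In the 15% example with full follow-up, the ITT difference is 0 and the estimate is 0/0.85 = 0, which is correct.

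Protocol 8.3, however, withdraws non-starters, SAP 4.6 handles withdrawals by an offset, and the outcome starts at day 8. A non-starter who leaves in week 1 may contribute no exposure. The observed difference is then already 8.5 days, and 8.5/0.85 = 10.0 days, which is worse than the per-protocol artefact.

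Best-case and worst-case bounds on those missing days (oral arm fully observed) put the XR-Bup rate between 0.85 × 0.6529 = 0.555 and 0.555 + 0.15 = 0.705. The ITT difference is then −7.2 to +16.9 days and the complier-average effect −8.5 to +19.9 days. Non-starters' data decide how useful the estimate is.

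**The case against.** A reader might infer that the exclusions can remove only XR-Bup participants, or that the check is bound to favour XR-Bup. The documents support neither.

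- *Only XR-Bup.* The list in 6.9 is open, and the protocol foresees missed oral dosing (6.3) and three consecutive uncollected doses (6.7.2). Protocol 5.1 still mentions new admissions, although 8.1, 8.3 and SAP 3.2 do not. Almost entirely is as far as the text goes.
- *Bound to favour XR-Bup.* No passage says that non-starters are less stable or less adherent. A participant doing well on low-dose methadone could decline to switch, and the direction then reverses.
- *Size.* Eligibility requires that the clinician expects conversion within 7 days (Protocol 8.1), and sites confirm that medication is in place before randomising (8.4), so non-starts may be few. If withdrawn non-starters contribute little exposure to the ITT model, removing them changes little.
- *Status.* The analysis is optional, so the conflict with 4.5 is between not planned and conditional. It does not touch the primary analysis.
- *Remedy.* A complier-average effect inherits the missing non-starter data. Its exclusion restriction is also open to doubt, because methadone participants allocated to XR-Bup are converted to Bup before any injection.

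All of this stands, and it limits the size and certainty of the point. It does not remove the one-sidedness of the exclusions or the disagreement between 4.5 and 6.9.

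**Conclusion.** The two exclusions apply a start-of-treatment test that in practice one arm faces, so the analysis does not compare like with like, whichever way the bias runs. It would favour XR-Bup if non-starters do worse than starters, by about 2.5 to 8.5 days against a 22.2-day target. That range assumes 5% to 15% non-starts, 30% abstinence among them and full follow-up. With r at 1 the bias is nil, and above 1 it reverses. The documents give neither the non-start rate nor the non-starters' outcomes.

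Separately, and without any assumption, SAP 4.5 and 6.9 disagree on whether the analysis is planned and on what triggers it, and the cross-reference to 6.5 is wrong. The ITT primary analysis is not in question.

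**What to change.** - Do not use the two one-sided exclusions as the adherence check. Prespecify instead a complier-average effect of receiving at least one XR-Bup injection, with randomisation as the instrument, centre and injecting status as covariates, and all randomised participants included. Non-compliance should be close to one-sided, since the injection is supplied through the trial and "The product is currently unlicensed in the EU" (Protocol 6.1).
- State how outcome days are handled for non-starters whom Protocol 8.3 withdraws. Use TLFB and UDS data from those willing to keep providing it (Protocol 8.5), with best-case and worst-case bounds for the rest. Without their data the estimate is no less biased than the exclusions.
- State the exclusion restriction, and note that conversion from methadone to Bup precedes any injection.
- Report non-starts and exclusions by arm.
- Drop the pooled 10% trigger, make 4.5 and 6.9 agree, and point 4.5 to 6.9.

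The cost is SAP wording and one further model using the Injection Log. The estimate will have a wider confidence interval than a naive per-protocol one, and it adds assumptions that must be stated.

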5.2. Trial design, blinding overview

EXPO is a pragmatic, multi-centre, open-label, superiority randomised controlled trial in NHS specialist addiction clinics delivering standard-of-care oral opioid medication for adults with OUD. The study will be implemented in five clinically recruiting sites (NHS trusts) across England and Scotland: in the coordinating centre in South London, the West Midlands, Greater Manchester, Newcastle and Tayside. The target randomised sample size is 604 patients. Recruitment will be in two study phases, as follows:

In **Phase 1** (all sites and with enrolment timed to start at approximately the same time), informed consenting participants will be allocated to one of two groups:

Group 1: XR-Bup (n=152; approx. n=38 at each site)

Group 2: Bup/Met (n=152; approx. n=38 at each site)

Participants in group 2 will receive Bup or Met following the local NHS clinical process of medical assessment and informed by any patient expressed preference for Bup or Met. All participants in groups 1 and 2 will receive standard case and medication management with general drug counselling (fortnightly, one-to-one at the clinic; ~30 minutes). The study plan is to aim to commence recruitment for groups 1 and 2 in July 2019 with all participants completing follow-ups in Q1 2020 (n=76 participants in each NHS trust)*.

During Phase 1 at the EXPO co-ordinating centre only, there will be allocation of participants to two additional groups:

Group 3: XR-Bup + PSI (South London site only)

Group 4: Bup/Met + PSI (South London site only)

All participants in groups 3 and 4 will receive standard case/medication management and general drug counselling, as usual. The PSI will be a tailored PSI (adapted from the co-ordinating centre's successful previous trial to develop this therapy (ARC Trial; ISRCTN69313751) and offered to participants across the treatment phase. At the co-ordinating centre, recruitment to groups 1-4 will commence in July 2019 using a 4:1 allocation ratio in favour of groups 1 and 2 (given local resource capacity)*.

In **Phase II** (co-ordinating centre only) there will be continued recruitment of groups 3 and 4 following completion of Phase I using a 1:1 allocation ratio until target quarter 3 2021, at which point it is aimed that all participants will have completed this phase*.

Group 3: XR-Bup + PSI (Total from Phase I and Phase II 150 South London site only)

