5.2 DEFINITIONS AND CALCULATIONS OF OUTCOME MEASURES

The following outcomes measures have been identified in relation to the objectives as described in section 3.2

Primary objective:

Objective 1 - effectiveness of BUP-XR and MET/BUP-SL

Measure 1; Number of days abstinent from 'substance' during days 8-168 (weeks 2 to 24, 161 days); combining self-report information from time-line follow-back interview adapted from the Treatment Outcomes Profile and incorporating data from 12 scheduled urine drug screens (UDS). The UDS results will provide biological verification for up to 36 out of the 161 days required.

- Days abstinent from illicit/non-medical opioids (Primary outcome)
- Days abstinent from cocaine (secondary outcome)
- Days abstinent from benzodiazepines (secondary outcome)

The primary outcome will be determined by combining the self-report results and UDS results to give an overall count for each participant. Where data is available for self-report and UDS, if the results are inconsistent the UDS data will override the self-report. Where this occurs, the result will overrule the self-report for the day of the UDS and the two days prior. Examples are indicated below.

Example 1

A negative self-report for 4 days, day 4 a positive UDS, figure 2 below.

	Day 1	day 2	Day 3	Day 4	Day 5	Day 6	Day 7	Day 8	Day 9	Day 10
Self-report	no drug use	no drug use	no drug use	no drug use	drug use					
UDS (Day 4)				positive						

Figure 2: Example 1 of Self-report and UDS results

The UDS would trump the 'no drug use' self-report for days 2 – 4, resulting the outcome in figure 3.

Outcome:	Day 1	day 2	Day 3	Day 4	Day 5	Day 6	Day 7	Day 8	Day 9	Day 10
	no drug use	drug use								

Figure 3: Self-report and UDS example 1 outcome

Example 2

A positive self-report for 2 days, day 4 a negative UDS as shown in figure 4.

	Day 1	day 2	Day 3	Day 4	Day 5	Day 6	Day 7	Day 8	Day 9	Day 10
Self-report	no drug use	no drug use	drug use							
UDS (Day 4)				negative						

Figure 4: Example 2 of Self-report and UDS results

The negative UDS would trump the self-report for days 2 – 4 (day 2 no change) resulting in the outcome below in figure 5.

Outcome:	Day 1	day 2	Day 3	Day 4	Day 5	Day 6	Day 7	Day 8	Day 9	Day 10
	no drug use	no drug use	no drug use	no drug use	drug use					

Figure 5: Self-report and UDS example 2 outcome

Example 3

UDS and self-report align figure 6, therefore no change to the outcome in figure 7

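### SAP 6.9 looks for pandemic-related missing data by enrolment period, but the disruption acts during follow-up, so the check uses a misclassified exposure

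*SAP*

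**What the plan says.** The COVID-19 part of SAP 6.9 uses one three-level variable, set by when a participant enrolled, for three purposes.

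- **Baseline description (firm).** "baseline characteristics will be summarised by enrolment period (pre Covid-19, during Covid-19, post Covid-19", to see whether the recruited population differed between periods.
- **Missing data (firm).** "Missing data will be assessed by 'pandemic enrolment period' to check whether there are any differences of missingness caused by the pandemic".
- **Model term (conditional).** "If deemed necessary sensitivity analysis adding 'pandemic enrolment period' into the model will be run".

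The SAP does not say on which dates the three periods begin and end.

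SAP 5.2 counts the primary outcome "during days 8-168 (weeks 2 to 24, 161 days"). SAP 6.9 also supplies the dates that matter here: "the pause in recruitment which occurred March 2020 to July 2020", an all-sites row in Table 3 with no screens over "2 nd April 2020 – 12 th June 2020", and national guidance of 22 May 2020 that changed dispensing for the oral arms. Protocol 5.2 gives the planned start: "The study plan is to aim to commence recruitment for groups 1 and 2 in July 2019". Neither document gives the actual start or enrolment counts by date.

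**The concern.** Enrolment date is the correct classifier for baseline characteristics, which are fixed at enrolment. It is the wrong one for events in the following 24 weeks. A participant enrolled in December 2019 keeps the pre label throughout, although the later part of that participant's outcome window lies in the pandemic.

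The pause in recruitment makes this worse. Nobody was being enrolled when screens stopped or when dispensing changed, so the people in follow-up at those moments had enrolled before the pause or at its start. With the boundary at the pause, the group that met the screen stop is the group labelled pre Covid-19.

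What is at stake is the interpretation of the missing-data check. The SAP presents it as a way to find missingness caused by the pandemic, and a comparison by enrolment label cannot carry that reading. The conditional model term inherits the same fault. As a main effect of enrolment period, it also cannot isolate a dispensing change that affected only the oral arms.

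**Working it through.** **Inputs from the documents**
- Outcome window: days 8 to 168 (SAP 5.2). Check: 168 − 8 + 1 = 161 days, as stated.
- Screens stopped 2 April 2020; the all-sites row runs to 12 June 2020 (SAP Table 3).
- Dispensing guidance 22 May 2020, oral arms (SAP 6.9).
- Recruitment pause March to July 2020 (SAP 6.9); planned start July 2019 (Protocol 5.2).

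**Assumptions, because the documents give no accrual data**
- Recruitment from 1 July 2019 up to, but not including, 20 March 2020: 263 enrolment days.
- Accrual even, rising linearly or falling linearly.
- Outcome day k falls k days after enrolment. The pre group is everyone enrolled before the pause.

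**Step 1: who finishes before screens stop.** Day 168 falls on 1 April 2020 for someone enrolled on 16 October 2019. So 108 enrolment days (1 July to 16 October) give no outcome day from 2 April, and 263 − 108 = 155 give at least one.

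**Step 2: share of the pre group with any outcome day from 2 April 2020**
- Even: 155/263 = 0.589, about 59%.
- Rising: 1 − (108 × 109)/(263 × 264) = 1 − 11,772/69,432 = 0.830, about 83%.
- Falling: (155 × 156)/(263 × 264) = 24,180/69,432 = 0.348, about 35%.

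A later start raises all three. From 1 October 2019 there are 171 enrolment days, of which 16 are unexposed:
- Even: 155/171 = 91%.
- Rising: 1 − (16 × 17)/(171 × 172) = 99%.
- Falling: (155 × 156)/(171 × 172) = 82%.

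**Step 3: share of outcome days (even accrual, 1 July start).** The 155 exposed enrolment days contribute 1, 2, …, 155 outcome days from 2 April.
- From 2 April onward: (155 × 156/2)/(263 × 161) = 12,090/42,343 = 0.286.
- From 2 April to 12 June only (72 days): (72 × 73/2 + 83 × 72)/42,343 = 8,604/42,343 = 0.203.

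**Step 4: effect on the planned comparison.** Let the ordinary missing-day rate be m, raised by d on affected days.
- *Rise persists from 2 April onward.* The pre group shows m + 0.29d and later enrollees show m + d. The observed difference is 0.71d, so it is diluted.
- *Rise is confined to 2 April to 12 June.* The pre group shows m + 0.20d. Later enrollees have no outcome days in that window and show m. The pre group then looks worse, which reverses the expected direction.

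**Step 5: can a different enrolment boundary repair it?** No. Under these rules, any boundary after 16 October 2019 can leave exposed people in the pre group. A boundary at that date would label as pandemic enrollees people recruited months before screens stopped, most of whose outcome days could precede 2 April. The two sides of the disruption lie within participants.

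**Step 6: site and arm.** Table 3 has monthly screens restarting in the intervention arm on 4 May (South London) and 7 May 2020 (Newcastle), but in the treatment-as-usual arm on 12 and 29 June. West Midlands restarts on 3 July and Manchester on 13 July. Tayside opened on 27 July 2020, so its participants all enrolled after screens stopped. Enrolment period hides these differences and partly reflects site mix.

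**The case against.** The best defence has four parts.

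1. **Screens are handled elsewhere.** Under SAP 4.6 a missing screen is not a missing outcome day, because self-report supplies it. SAP 6.9 also plans a best-case/worst-case analysis for every missing screen, whatever the enrolment label. This stands for screens. It does not show whether missed visits or missing self-report days rose during the pandemic, and it does not touch dispensing.

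2. **The baseline use is correct and the model term is conditional.** Both are true. The firm commitment at fault is the missing-data comparison.

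3. **The labels are accurate as enrolment labels, and the boundaries are undefined.** Also true. The fault lies in reading an enrolment label as exposure during follow-up, and the missing boundaries need stating in any case.

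4. **The randomised comparison is not shown to be affected.** Agreed. Nothing here demonstrates bias in the primary estimate.

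Four stronger readings are tempting, and the documents do not support them.

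- A reader might infer that most participants coded pre Covid-19 had disrupted follow-up. That depends on an accrual curve that is not given: it fails under falling accrual from 1 July 2019 (35%). The measure also counts a single day. Under even accrual from that start, about 71% of the group's outcome days precede 2 April 2020.
- A reader might infer that the dispensing change reached everyone in follow-up. SAP 6.9 confines it to the oral arms.
- A reader might infer that a null table would lead the SAP to declare the pandemic unimportant. No such decision rule exists; missing data are handled under SAP 4.6 whatever the table shows.
- A reader might think that cutting follow-up at 2 April and 22 May 2020 is enough. Open-ended cuts would pool the screen stop with all later follow-up, ignore the restart dates by site and arm, and confound period with time since randomisation.

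**Conclusion.** The point holds for the planned missing-data check and, if it is run, for the pandemic sensitivity model. Enrolment period misclassifies exposure to events during follow-up, and the SAP's own dates place the screen stop and the dispensing change inside the recruitment pause. That much needs no accrual assumption, beyond taking the pause as the boundary of the pre group.

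The size is uncertain. With a 1 July 2019 start and a 20 March 2020 stop, 35% to 83% of the pre group have at least one outcome day from 2 April 2020, with 59% under even accrual. A later start gives more. The consequence is a check that may mislead in either direction. The primary model is untouched. The change should be made because the present check cannot answer the question set for it and the correction is cheap.

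**What to change.** In SAP 6.9:

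1. Keep enrolment period for the baseline tables only, and state the calendar boundaries.
2. Tabulate missing self-report days, visits and screens by the calendar date of the scheduled day or visit, by arm and site. Use the periods in Table 3: before 2 April 2020, no screens, and monthly screens from each site's and arm's restart date. First reconcile the all-sites row with the earlier intervention-arm restarts at South London and Newcastle.
3. For the oral arms, add the dispensing period from 22 May 2020. Give the date of the later guidance that restored case-by-case decisions, which the SAP mentions without a date.
4. If the pandemic sensitivity model is run, replace enrolment period with calendar period of follow-up. Use one row per participant per period, with its own count of abstinent days and its own offset for days observed, and cluster standard errors on participant. Adjust for time since randomisation (for example, the mean study day of the row) and include a treatment-by-period term.

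**Cost.** Revised SAP wording and a little more derivation. The time-line follow-back is recorded by day (Protocol 9.1), and SAP 4.6 already uses an offset for unequal exposure. Some site-by-arm cells will be small, so the tables should be descriptive. No new data are needed.
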